ED-to-community care transitions for persons living with dementia and care partners: development, implementation, and pilot testing of a novel artificial intelligence + care coach intervention

Protocol Number

2000032226

NCT05352399

Protocol Version

05/31/2023

#4

PRINCIPAL INVESTIGATOR:

*Name: [name] MD MHS
Department: Emergency Medicine
[contact]
Email Address: [contact]*

REVISION HISTORY:

Revision #	Version Date
1	02/19/2022
2	03/31/2022
3	04/15/2022
4	05/31/2023

Synopsis

Primary Objective

The primary objective is develop and test NeuViCare AI + care coach as an intervention for ED-to-community care transitions for PLWD and their care partners, offering a potential solution to the lack of existing ED care transition interventions.

Secondary Objective (if applicable)

N/A

Study Duration

August 2022 – February 2024

Study Design

Overall, we will use a sequential exploratory mixed-methods approach with integration of Specific Aims at the study design level. We will use a two-phase qualitative approach within Specific Aim 1, including: 1) semi-structured interviews with stakeholders, and 2) AI design optimization through a design thinking workshop. Specific Aim 2 will use a quantitative approach to assess implementation and patient-centered outcomes in a quantitative survey-based fashion through a one-arm open-labeled trial to primarily assess functionality and usability.

Number of Study Sites

EDs at York St. Campus, Saint Raphael Campus, Shoreline Campus, and Bridgeport Campus

Study Population

For the older adult participants, the inclusion criteria will be: 1) age ≥ 65 years with a diagnosis of ADRD or dementia within the electronic health record OR new cognitive impairment identified during an ED visit, 2) be fluent in English or Spanish, 3) discharge to the community setting after an ED visit, and 4) be willing to engage in discussions regarding the implementation of a novel AI technology. Primary care partners of PLWD must possess a smart device (either a phone, tablet, or computer) that has internet access to utilize and interact with NeuViCare AI services.

Number of Participants

55

Primary Outcome Variables

After in-ED enrollment, we will collect baseline measurements of PLWD and their care partners. Particularly, at time 0 this will include domain assessments of validated tools

addressing dementia knowledge, PLWD self-efficacy, psychological well-being, social connectedness, and caregiver experience. After ED- or hospital-community care transition, a virtual session led by the care coach will build upon discharge instructions by developing a comprehensive transdisciplinary care plan and integrating the use of NeuViCare AI technology. Subsequent sessions with the PLWD and their care partner will assess knowledge translation of NeuviCare AI, follow through with care plan, and the development of sustainable skills for preventing crisis and recidivism. At follow-up time points of 7 days, 30 days, and 3 months, participants will be contacted to reassess responses to above domains of interest (primary outcome).

Secondary and Exploratory Outcome Variables (if applicable)

Participants will be measured regarding their healthcare utilization, including ED visits, hospitalizations and care plan adherence with follow-up in the outpatient setting (secondary outcome). Finally, implementation outcomes of the NeuViCare AI technology will be assessed through validated surveys of acceptability, appropriateness, feasibility, and usability (secondary outcome).

Abbreviations

Abbreviation	Explanation
--------------	-------------

Glossary of Terms

Glossary	Explanation
----------	-------------

Table of Contents

Preface.....	2
Synopsis	4
Primary Objective	4
Secondary Objective (if applicable).....	4
Study Duration.....	4
Study Design	4
Number of Study Sites	4
Study Population	5
Number of Participants.....	5
Primary Outcome Variables	5
Secondary and Exploratory Outcome Variables (if applicable).....	5
Abbreviations	6
Glossary of Terms.....	7
1 Introduction	11
1.1 Introductory Statement	11
2 Background.....	12
2.1.1 Device Preclinical Experience	12
2.1.2 Device Clinical Experience	12
2.2 Background/prevalence of research topic	12
3 Rationale/Significance	13
3.1 Problem Statement.....	13
3.2 Purpose of Study/Potential Impact	13
3.2.1 Potential Risks.....	13
3.2.2 Potential Benefits	13
4 Study Objectives.....	14
4.1 Hypothesis	14
4.2 Primary Objective	14
4.3 Secondary Objectives (if applicable)	14
5 Study Design	15
5.1 General Design Description.....	15

5.1.1	Study Date Range and Duration	15
5.1.2	Number of Study Sites	15
5.2	Outcome Variables	15
5.2.1	Primary Outcome Variables	15
5.2.2	Secondary and Exploratory Outcome Variables (if applicable)	15
5.3	Study Population	15
5.3.1	Number of Participants	16

1.1 Introductory Statement

This document is a protocol for a human research study. The purpose of this protocol is to ensure that this study is to be conducted according to ICH GCP guidelines, and according to CFR 21 Part 812, other applicable government regulations, and Institutional research policies and procedures.

2 Background

2.1.1 Device Preclinical Experience

As a way to address many of these unmet caregivers' needs and poor patient outcomes, Amicus Brain Innovations, Inc. a technology start-up company, has created NeuViCare, which is a soon-to-be commercially available AI-led, assistive and decision support online service application that can be accessed from a smart phone, tablet or computer by clinicians, patients and caregivers. It was designed to reduce caregiver load and increase patient adherence rates for better quality of life.

NeuViCare's multifunctional platform services are designed to impact caregiver load, while addressing their unmet needs and patients' quality of life through AI-led technology.

NeuViCare Task-Support Service will increase care plan adherence rates and allow for more timely diagnoses by providing an interactive, appointment reminder service. NeuViCare Resource Advisor will educate caregivers about available resources and reduce their time spent on this task by providing context-sensitive, task-support services to reliable community resources. NeuViCare Community will provide a secure, online forum that will provide peer-support and increase caregivers knowledge on challenging behaviors by administering weekly educational series and just-in time answers provided by AI. Amicus Brain will provide technical support and troubleshoot any issues with the community software.

2.1.2 Device Clinical Experience

Given the potential impact of NeuViCare in improving quality of care, Amicus Brain and Yale Memory Clinic have previously partnered together to successfully pilot test NeuViCare's impact on patient care in the outpatient Neurology setting.

2.2 Background/prevalence of research topic

As the nation's older adult population grows, Alzheimer's Disease and Alzheimer's Disease-Related Dementias (AD/ADR) is projected to affect an estimated 12.7 million people by 2050. Attention has been drawn to the growing population of persons living with dementia (PLWD) and their care partners through the National Plan to Address AD, yet physical, psychological, and financial burdens have persisted for the estimated 21.6 million unpaid informal care partners (e.g. family, friends). Often at considerable personal cost, care partners play an integral role in ensuring success of care transitions across healthcare settings, particularly involving the emergency department (ED). With the majority of PLWDs being discharged from the ED, care partners subsequently provide a significant amount of hands-on care and navigation of health-related and social needs within this vulnerable time period. Highlighting the inadequacies of current care transition efforts, PLWDs visit the ED at a higher rate and also have higher ED return and mortality rates after an initial ED visit in comparison to their non-cognitively impaired counterparts. The prioritization of ED dementia

care research by the American Geriatrics Society, the widespread dissemination of the 2014 consensus geriatric ED guidelines, and the 2018 launch of a geriatric ED accreditation program have highlighted the need for evidence with best practices for PLWD and their care partners. All prioritize the importance of ED-to-community care transitions, yet effective interventions focusing on patient- and care partner-centered outcomes are largely lacking. With uncertainty regarding treatment options for PLWD, there is an urgent need and opportunity to develop interventions addressing ED-to-community care transitions.

To date, little data exist on effective interventions to improve ED-to-community care transitions for older adults with ADRD or cognitive impairment. Attempts have primarily focused on cognitively intact older adults and considered the use of comprehensive geriatric assessments, enhanced discharge planning, referrals to specialist services, or community paramedics with variable impact on ED revisits and overall limited attention to patient-centered outcomes. Traditionally, some of these 'high touch' modalities involve frequent check-ins by healthcare personnel to ensure care plan adherence, but are resource-intensive, and therefore may have limitations in the way of scalability and affordability. Technology, including artificial intelligence (AI), has been shown to be a 'high tech' advancement that offers the potential to benefit older adults by promoting self-service and independence. AI has proven to be acceptable and used by older adults and care partners in relation to healthcare needs, but has been incorporated less within ED populations.

3 Rationale/Significance

3.1 Problem Statement

As the nation's older adult population grows, Alzheimer's Disease and Alzheimer's Disease-Related Dementias (AD/ADR) is projected to affect an estimated 12.7 million people by 2050. With the majority of PLWDs being discharged from the ED,¹⁴ care partners subsequently provide a significant amount of hands-on care and navigation of health-related and social needs within this vulnerable time period. To date, little data exist on effective interventions to improve ED-to-community care transitions for older adults with ADRD or cognitive impairment. Technology, including artificial intelligence (AI), has been shown to be a 'high tech' advancement that offers the potential to benefit older adults by promoting self-service and independence. AI has proven to be acceptable and used by older adults and care partners in relation to healthcare needs, but has been incorporated less within ED populations.

3.2 Purpose of Study/Potential Impact

Incorporation of AI-led technology among PLWD and their care partners will provide new insights into ways in which the ED discharge process can be improved. Additionally, this work will provide information regarding the optimal interaction between AI + care coaching to support this essential population during ED-to-community care transitions. Together, the proposed research will provide high-quality evidence regarding the design optimization and feasibility of implementing a novel 'high tech – high touch' ED-to-community care transition intervention among PLWD and their care partners.

3.2.1 Potential Risks

This risks to human subjects in the proposed research are minimal. Specific Aim 1 involves qualitative interviews and a design thinking workshop with various stakeholders regarding the role of AI + care coaching during ED-to-home community care transitions. Specific Aim 2 involves the pilot testing of the NeuViCare AI. Psychologically, there is a risk that participants will find the interviews and engagement with the AI + care coach burdensome or distressing. There is also a risk of inadvertent release of potentially identifying information. Other physical, social, cultural, financial, and legal risks are minimal. Data collection, management, and analytic processes outlined in the proposal are designed to ensure that participant privacy and confidentiality will be maintained.

3.2.2 Potential Benefits

Results from this study will help us learn more about ED-to-community care transitions of PLWD and their care partners. We believe that the possible benefits for clinical care outweigh the minimal risks of the proposed research. A small incentive will be provided, and the participants may benefit directly from the AI + care coach intervention, particularly if the

hypothesis is proven correct. This could be due to increased access to support and manifest in the way of increased engagement in the care plan, reduced care partner burden, and reduced health utilization in the following 30 days.

4 Study Objectives

4.1 Hypothesis

Specific Aim 1: We will optimize the NeuViCare AI + care coach intervention, for subsequent pilot testing.

Specific Aim 2: We will demonstrate: 1) feasible and acceptable implementation of NeuViCare AI + care coach intervention, 2) care plan adherence and NeuViCare AI engagement, and 3) reduced 30-day care partner burden and PLWD healthcare utilization.

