5.2 Outcome Variables

5.2.1 Primary Outcome Variables

After in-ED enrollment, we will collect baseline measurements of PLWD and their care partners. Particularly, at time 0 this will include domain assessments of validated tools addressing dementia knowledge, PLWD self-efficacy, psychological well-being, social connectedness, and caregiver experience. After ED- or hospital-community care transition, a virtual session led by the care coach will build upon discharge instructions by developing a comprehensive transdisciplinary care plan and integrating the use of NeuViCare AI technology. Subsequent sessions with the PLWD and their care partner will assess knowledge translation of NeuviCare AI, follow through with care plan, and the development of sustainable skills for preventing crisis and recidivism. At follow-up time points of 7 days, 30 days, and 3 months, participants will be contacted to reassess responses to above domains of interest (primary outcome).

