5.2.2 Secondary and Exploratory Outcome Variables (if applicable)

Participants will be measured regarding their healthcare utilization, including ED visits, hospitalizations and care plan adherence with follow-up in the outpatient setting (secondary outcome). Finally, implementation outcomes of the NeuViCare AI technology will be

assessed through validated surveys of acceptability, appropriateness, feasibility, and usability (secondary outcome).

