5.3.1 Number of Participants

Phase 1 (qualitative interviews) – approximately 15

Phase 2 (Design Thinking Workshop) – approximately 15

Pilot Implementation – approximately 25

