5.3.2 Eligibility Criteria/Vulnerable Populations

For the older adult participants, the inclusion criteria will be: 1) age ≥ 65 years with a diagnosis of ADRD or dementia within the electronic health record OR new cognitive impairment identified during an ED visit, 2) be fluent in English or Spanish, 3) discharge to the community setting after an ED visit, and 4) be willing to engage in discussions regarding the implementation of a novel AI technology. Primary care partners of PLWD must possess a smart device (either a phone, tablet, or computer) that has internet access to utilize and interact with NeuViCare AI services.

6 Methods

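### Section 4.1 lists reduced 30-day PLWD healthcare utilization among the things Aim 2 will demonstrate, but the plan gives utilization no comparator and no window and analyses it only descriptively.

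*Combined protocol and SAP*

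**What the plan says.** Section 4.1 sets out three things that Aim 2 is to demonstrate. The third is "reduced 30-day care partner burden and PLWD healthcare utilization".

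Other sections that bear on the utilization half of that item:

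- **Design.** The synopsis (Study Design) describes a "one-arm open-labeled trial to primarily assess functionality and usability". Section 6.1.3 (assignment/randomization) is N/A.
- **Outcome.** Section 5.2.2 makes utilization secondary: "Participants will be measured regarding their healthcare utilization, including ED visits, hospitalizations and care plan adherence". It gives no window, look-back or reference rate.
- **Baseline.** The time-0 domains named in 5.2.1 are "dementia knowledge, PLWD self-efficacy, psychological well-being, social connectedness, and caregiver experience". Prior utilization is not named.
- **Background.** Section 2.2 says that "PLWDs visit the ED at a higher rate and also have higher ED return and mortality rates after an initial ED visit", compared with people without cognitive impairment, but gives no rate.
- **Analysis.** Section 6.4.1 assigns descriptive statistics to ED and hospitalization outcomes, citing the pilot nature of the work. Sections 6.4.3.1 and 6.4.3.2 only refer back to it. Care partner burden (Zarit) is treated differently: baseline and 30-day means are compared by a paired t-test.
- **Follow-up.** Sections 6.3.5 and 6.3.6 follow participants for 3 months after the ED visit.
- **Benefits.** Section 3.2.2 links possible direct benefit to the case where the "hypothesis is proven correct", and lists lower 30-day utilization among the ways it might appear.

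**The concern.** A reduction is a comparison, and for utilization the plan names nothing to compare with. A descriptive ED-visit rate from one treated group can be high or low, but it cannot be reduced without a second quantity beside it. The hypothesis therefore promises a conclusion that the planned analysis does not produce.

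The window adds to this. The hypothesis refers to 30 days, the outcome definition and the analysis text give utilization no window, and data run to 3 months. An analyst could report either period as the answer to 4.1, and could choose after seeing the data.

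At stake is what the report may claim. Section 6.3.1 schedules grant applications and dissemination from the results, so an unsupported statement of reduced utilization could be carried forward as a pilot finding.

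**Working it through.** The plan gives no event rate, effect size, alpha or power for utilization, and 6.4.2 is N/A, so there is no calculation to reproduce. The planned numbers do add up: 15 + 15 + 25 = 55, as in the synopsis.

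**Step 1. Look for a comparator in each place one could stand.**

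| Possible comparator | Where it would be | What is there |
|---|---|---|
| Control group | Synopsis, 6.1.3 | One arm; assignment N/A |
| Pre-period | 5.2.1, 5.2.2 | None specified |
| Reference rate | 2.2, 5.2.2 | Direction only, no number |
| Comparative analysis | 6.4.1, 6.4.3 | Descriptive statistics only |

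The burden half of the same sentence differs: it has a baseline, a 30-day value and a test.

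**Step 2. Look for the window.** For utilization, 30 days appears in 3.2.2 and 4.1 only. The 30-day point in 5.2.1 belongs to the survey domains, and the one in 6.4.1 to the DKAS and Zarit scores.

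**Step 3. What the descriptive analysis can give.** Input: "Pilot Implementation – approximately 25" (5.3.1). The event counts are illustrative, because the documents give no rate. The exact (Clopper-Pearson) 95% interval for x of n has lower limit Beta(0.025; x, n − x + 1) and upper limit Beta(0.975; x + 1, n − x).

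- 2/25 (8%): 1.0% to 26.0%
- 5/25 (20%): 6.8% to 40.7%
- 10/25 (40%): 21.1% to 61.3%

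The widest half-width at n = 25 is 20 percentage points. If the 25 count both members of each pair, there are about 12 PLWD (25/2 = 12.5), and the widest half-width is 29 points.

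**Step 4. Would adding a reference rate be enough?** Assume a fixed reference p0 and an exact one-sided test at nominal 0.05, n = 25, which declares a reduction if the count is at most c, where c is the largest value with P(X ≤ c | p0) ≤ 0.05.

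| Assumed p0 | c | Attained alpha | Power, rate halved | Power, rate cut by a quarter |
|---|---|---|---|---|
| 20% | 1 | 0.027 | 27% | 9% |
| 30% | 3 | 0.033 | 47% | 15% |
| 40% | 5 | 0.029 | 62% | 19% |

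Over this assumed range, naming a reference rate would not give usual power even for a halving. That favours changing the claim over adding a test. The finding itself rests on steps 1 and 2 and needs none of these rates.

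**The case against.** The strongest defence is that this is a pilot and the sentence is a hypothesis. Aim 1 in 4.1 is written in the same promissory style. The synopsis limits the main purpose to functionality and usability, utilization is secondary, no decision rule depends on it, and 6.4.1 gives the pilot nature as its reason for describing and not testing. All of this stands, and it limits the seriousness of the point. The descriptive analysis is reasonable. It does not rescue the wording, because a hypothesis should still be one the plan can address.

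A second defence is that a baseline might be obtainable. Section 5.2.1 does not present its time-0 list as complete, and 7.6 and 7.9 mention a chart review step. That is fair, so the absence of utilization from the list is weak evidence on its own. But no section says that the chart review collects earlier visits, and none plans a before-after comparison.

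A reader might infer three stronger things that the documents do not support:

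- **That the burden hypothesis is equally untestable.** It is not: the paired t-test addresses a within-group 30-day change. What it cannot do, without a control group and with a baseline at or soon after an ED visit, is attribute that change to the intervention.
- **That the plan would produce a false fall in ED visits by comparing with a period containing the index visit.** No such pre-period is planned.
- **That 30 days is undefined throughout.** The gap concerns utilization only.

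**Conclusion.** The point holds for utilization. Section 4.1 states a conclusion that the one-arm design and the descriptive analysis in 6.4.1 cannot deliver, and the 30-day window in that conclusion is not carried into the outcome definition or the analysis. This follows from the text and needs no assumed rate. The interval widths in step 3 assume 25 (or about 12) PLWD with complete data, and their event counts are illustrative.

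It should be fixed, but it is a limited fault: one over-strong claim on a secondary outcome. The assessment of functionality and usability is unaffected, and the burden comparison stands as a within-group change.

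**What to change.** 1. **Section 4.1.** Take utilization out of the list of things to be demonstrated and add a separate sentence: *We will describe 30-day ED-visit and hospitalization rates with exact 95% CIs.* Keep the burden hypothesis, worded as a within-group change from baseline to 30 days, so that it matches the planned t-test.
2. **Section 6.4.1, window.** State that utilization is counted over 30 days from one defined start point, for example discharge to the community from the index episode, applied alike to participants recruited in the ED and by telephone. This matters because 6.3.2 allows telephone recruitment after discharge, so discharge and enrolment dates can differ.
3. **Section 6.4.1, index episode.** Exclude the index ED visit and any admission that is part of it. Eligibility (5.3.2) requires "discharge to the community setting after an ED visit", so every PLWD has an index visit, and 5.2.1 allows the transition home to start from hospital, so some may also have an index admission.
4. **Section 6.4.1, interpretation.** Add that, without a control group, neither the utilization rates nor the change in burden will be interpreted as an intervention effect.
5. **Section 3.2.2.** Align the reference to the hypothesis with the reworded 4.1.

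The cost is wording in three sections plus intervals on results already planned. No new data, procedures or participants are needed. The downside is a less favourable stated claim.
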